### **5.2.2 Consenting process:**

The PI or a designated physician co-investigator will follow-up the preliminary discussion to answer any additional questions and obtain written authorization and consent for participation from subjects or their LAR. The investigator or a co-investigator will discuss the nature of the research study and study procedures with the participant or LAR inclusive of the risks and potential benefits of study participation. In cases where the LAR is not present in the hospital, the study will be discussed over the telephone. If the LAR agrees, the consent form (ICF) will be e-mailed or faxed to the number provided by the LAR. No research activities can start before the signed document is received from the LAR. The PI or any physician investigator who discussed the study by phone must sign, date, and time the consent form when it is received (date/time of receipt, not the date of discussion).

Pennsylvania law defines no specific surrogate decision maker for health care. However, if consent is obtained from a surrogate decision maker, the basis for establishing his/her identity should be one of the following: Durable Power of Attorney for Health Care, next of kin, or following lines of sanguinity in order of relationship (i.e., court appointed guardian, spouse, natural or adoptive parent, adult child, adult sibling, any other available adult relative related through blood or marriage known and documented to have made decisions for the subject in prior health care settings).

Rights as a research subject will be explained and ample time for the participant or LAR to review the consent document prior to obtaining written signature of informed consent will be given. After this detailed discussion of the study and conclusion of any questions, the study investigator and/or co-investigator will obtain informed consent with documentation of the consenting process, prior to beginning any research activities. All participants and LARs will be informed of their right to withdraw the patients from study participation at any time. Additionally, enrolled patients will have the right to withdraw from the study once decision-making capacity is regained if the patients recover quickly from their acute illness (e.g. with early liberation from the ventilator while the patient is still in the study).

After consent, the pre-entry procedures include those listed in Section 5.4.2. Pre-entry evaluations must be completed within 12 hours prior to study entry.

### **5.2.3 Baseline evaluation and randomization:**

If pre-entry evaluation is acceptable, the participant will be enrolled in the study and undergo baseline testing included in Section 5.4.3. At that point, the participants will be randomized to interventional and placebo control arms. Enrollment into interventional and placebo arms will be stratified at one level by the presence or absence of pre-existing self-reported diabetes mellitus utilizing separate randomization tables. The University of Pittsburgh Medical Center Investigational Drug Service (UPMC-IDS) will be responsible for randomization, blinding, and providing the study infusion at the bedside to the clinical team.

#### **5.2.4 Blinding:**

The UPMC-IDS will dispense investigational infusions that conceal infusion contents with an opaque cover, thus the treating ICU clinicians, nursing staff, and study investigators will be blinded to group allocation. Group allocation will remain concealed until blinding is broken after final data analysis is completed.

### **5.3 Study treatment**

#### **5.3.1 Treatment arms**

At study entry, the participant will be randomized into an interventional arm that will receive an enteral dextrose infusion or a control arm that will receive enteral free water placebo.

**1a: Enteral dextrose infusion:** A standard solution of 50% Dextrose (0.85 kcal/mL) will be initiated within 48 hours of meeting sepsis criteria and will be infused at 10 mL per hour for 24 hours. For a participant that would have an expected daily caloric requirement of 2000 kcal per day, enteral dextrose infusion would deliver approximately 20% of the daily caloric need. As a reference, the enteral tube formulation Jevity 1.2 provides 1.2 kcal/mL and is often infused at 10 mL per hour upon initiation of enteral tube feeding. Thus the volume and level of delivered calories in the study group will be similar to the amount delivered in low level enteral tube feed formulations.

**1b. Placebo control:** Patients in the placebo control arm will receive enteral free water at a rate of 10 mL per hour following randomization to control for the effects of an enteral infusion. Although these participants will not receive any enteral calories, a retrospective review of critically ill patients admitted to the Acute Lung Injury Registry at the University of Pittsburgh with a patient population similar to the patients we will enroll to this study revealed that (1) less than 10% of patients receive any enteral infusions in the first 48 hours of ICU admission, (2) greater than 50% of calories are delivered in intravenous infusions rather than the enteral route, and (3) total level of caloric support in the absence of enteral feeding is approximately 10-15% of daily caloric needs.

#### **5.3.2 Study drug**

**Dextrose infusion:** 50% Dextrose solution will be infused via an oro/nasogastric tube by ICU nursing personnel per standard practices. The solution will be prepared and provided by the IDS and will be infused at a rate of 10 mL per hour for 24hr through a standard enteral nutrition pump. No additional water flushing will be necessary. Interruption/discontinuation of the infusion will be at the discretion of the treating physicians. Symptoms/signs of intolerance including vomiting or aspiration will be considered an adverse event. Gastric residuals will not be checked monitored in this study as they are not required per current critical care guidelines.

### **5.3.3 Study duration**

Study treatment will be administered for a total of 24 hrs. Subsequent decisions for type/rate of enteral nutrition following the 24hrs will be at the discretion of the medical ICU team.

### **5.3.4 Study product formulation and storage**

50% Dextrose solution and free water solution will be stored at room temperature in a dry place

### **5.3.5 Pharmacy role**

The UPMC-IDS will be responsible for (1) preparation of 50% Dextrose and free water solutions, (2) randomization of participants into intervention and placebo groups, and (3) distribution of intervention solutions such that clinical team and investigators are blinded to group allocation.

## **5.4 Study exams and procedures**

Study exams are described below and in Table 5.1.

### **5.4.1 Initial screening (pre-consent)**

- Review of admission documentation in ICU and assessment of eligibility.

### **5.4.2 Pre-entry evaluation and consent**

- Clinical assessment
- Medical history
- Informed consent

### **5.4.3 Baseline testing and randomization**

- Baseline clinical variable recording
- Pre-intervention capillary blood glucose measurement
- Initial research blood draw (up to 4 hours prior to the start of infusion)
- Aerodigestive tract samples for microbiome analyses (up to 4 hours prior to the start of infusion):
  - Oral swab
  - Tracheal aspirate (if the patient is on mechanical ventilation)
  - Gastric aspirate
- Colonic tract samples for microbiome analyses (up to 4 hours prior to the start of infusion)
  - Rectal swab
  - Stool sample (if available)

### **5.4.4 Study period**

- Initiation of study interventions as per protocol for 24 hrs
- Hemodynamic monitoring per ICU protocol
- Capillary blood glucose approximately every 6 hours

### **5.4.5 Mid-intervention assessment**

- Clinical assessment by study team member to monitor status and tolerance to infusion to be performed 12 hours after the start of infusion +/- 4 hours

#### 5.4.6 Intervention conclusion – End of infusion period

- Second research blood draw (up to 2 hours prior to the end of infusion or ½ hour after)
- Repeat aerodigestive tract samples for microbiome analyses (+/- 2 hours to the end of infusion):
  - Oral swab
  - Tracheal aspirate (if the patient is on mechanical ventilation)
  - Gastric aspirate
- Repeat colonic tract samples for microbiome analyses (+/- 2 hours to the end of infusion)
  - Rectal swab
  - Stool sample (if available)

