## 1.0 SYNOPSIS

Design	The study is a prospective randomized double-blinded placebo-controlled clinical trial to test the effects of early enteral dextrose as a therapeutic agent in critically ill patients with sepsis. Primary outcomes are differences in circulating plasma levels of the pro-inflammatory cytokine IL-6 to be tested 24 hours after randomization. Secondary outcomes include differences in circulating incretin hormone levels, differences in other pro-inflammatory cytokines including IL-1 $\beta$ and TNF- $\alpha$ , changes in intestinal microbial composition and function after intervention, glycemic control and variability as assessed by capillary blood glucose measurements and exogenous insulin dosing during the intervention period, and clinical outcomes including intensive care unit (ICU) and hospital stay and in-hospital mortality.
Duration	Study participants will be randomized within 48 hours of meeting sepsis criteria, undergo a 24 hour intervention and data collection period, and will be followed for clinical outcomes.
Sample Size	72 participants (36 patients in each arm)
Population	Men and women older than 18 years of age with evidence of sepsis admitted to the intensive care unit with an existing enteral feeding tube (or with imminent plans to place one).
Regimen	Participants will be randomized to either receive early low level enteral infusion of dextrose (intervention) or enteral free water (placebo control).

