## 5.0 RESEARCH DESIGN AND METHODS

This study is a single-center, prospective, double-blinded, randomized placebo-controlled clinical trial to determine the therapeutic effects of early enteral dextrose in critically ill patients admitted with sepsis. This trial will have an interventional arm in which participants receive a low level enteral dextrose infusion and a placebo control arm in which participants will receive an enteral free water infusion. The primary outcome of this study is the extent of systemic inflammation as determined by circulating levels of the pro-inflammatory cytokines IL-6 measured at the end of the intervention. Secondary outcomes include measures of glycemic control by capillary blood glucose; measures of insulin, C-peptide, and the incretin hormones glucose-dependent insulinotropic peptide (GIP) and glucagon-like peptide-1 (GLP-1); measures of other pro-inflammatory cytokines including IL-1 $\beta$  and TNF- $\alpha$ ; determination of the composition and function of the aerodigestive tract and colonic microbiome; and clinical measures (including incidence of emesis, ICU length of stay, hospital length of stay, mortality).

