**Table 5-1. Schedule of Procedures**

	Pre-Entry	Screen	Baseline	Study Period	12 hrs	24 hrs	Day 7	Day 30
Documentation of Sepsis	X							
Medical Review for Inclusion/Exclusion	X	X						
Informed Consent		X						
Baseline Characteristic Measurement		X	X					
Clinical Assessment			X		X	X		
Blood Glucose Measurement			X	X				
Research Infusion				X				
Research Blood Draw			X			X		
Microbiome sampling			X			X	X	
Review of Electronic Medical Record			X			X	X	X

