#### 6.3.2 Research blood draws

Blood will be drawn for plasma and serum at two time points (a) at the time of randomization and (b) after the completion of the intervention period. Approximately 10 mL of blood will be drawn each time either by venipuncture or by drawing blood from existing indwelling catheters (central venous lines or arterial lines) by the patient's bedside nurse. Blood will be drawn into several tubes including serum, EDTA, and BD P800 collection tubes.

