#### 6.3.3 Microbiome sampling

Aerodigestive and colonic tract samples will be collected as follows at baseline, at the end of the infusion period, and at day 7:

**Oral swabs:** A swab will be gently rubbed on the tongue dorsum, the hard palate, the buccal mucosa, and the gingiva. Specimens will be secured in a sterile tube and stored in a locked freezer until bacterial nucleic acid extraction procedures. The procedure will be performed twice in order to obtain samples for both bacterial DNA and RNA extractions.

**Tracheal aspirates:** Five to 10 ml of tracheal aspirates will be collected using a sterile catheter during endotracheal tube suctioning if the patient remains on mechanical ventilation for the study period. Samples are collected according to standardized protocols by trained respiratory therapists. Such samples are typically collected as part of routine clinical care, but are usually discarded. Samples will be transported immediately in wet ice. Sample aliquots are stored at -80°C in a locked freezer until bacterial nucleic extraction procedures.

**Gastric aspirates:** Ten to 20 ml of gastric aspirates will be collected through the existing feeding tube. A first sample of gastric aspirate will be collected prior to initiation of experimental infusions. If no gastric aspirate obtained, then instillation of approximately 20 mL of water through the feeding tube will be performed for suctioning an adequate amount of gastric aspirate, which will be placed in a sterile specimen cup and then stored at -80°C in a locked freezer until bacterial nucleic acid extraction procedures. At 24 hr, we will obtain a gastric aspirate of 10-20 mL, again stored in similar fashion. At day 7, we will obtain a similar specimen if a feeding tube is still in place and the patient remains in the ICU.

**Stool samples:** If stool is available, a portion of the sample will be taken and stored in a sterile specimen cup, as above.

**Rectal swabs:** A swab will be gently advanced through the anal sphincter in the anal vault and gently rubbed on the rectal mucosa. Specimens will be secured in a sterile tube and stored at -80°C in a locked freezer until bacterial nucleic acid extraction procedures. The procedure will be performed twice in order to obtain samples for both bacterial DNA and RNA extractions.

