## **7.5 Protocol adherence**

Participants in both the placebo and intervention group will be assessed to determine the (1) the number of interruptions in enteral study infusion and (2) total amount of time that enteral study infusion was successfully administered during the 24 hour intervention period.

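### The primary IL-6 draw has no single clock time, and sampling after an early stop of the infusion is stated only for patients who start tube feeds

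*Combined protocol and SAP*

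**What the plan says.** The time of the primary sample is given in five places:

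- Synopsis: "IL-6 to be tested 24 hours after randomization".
- Section 5.0: "measured at the end of the intervention".
- Section 5.4.6: "Second research blood draw (up to 2 hours prior to the end of infusion", with the window closing half an hour after that end.
- Section 6.3.2: "after the completion of the intervention period".
- Table 5-1: the row "Research Blood Draw" is marked in a 24-hour column that names no time zero.

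The planned length is clear: "Study treatment will be administered for a total of 24 hrs" (section 5.3.3).

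Several events can pause or end the infusion sooner. The treating physicians may interrupt or stop it (5.3.2). Emesis pauses it until it is restarted under ICU guidelines (7.1.1). Diabetic ketoacidosis or hyperosmolar syndrome ends it (7.1.2). Section 7.4 lists further criteria, and starting tube feeds ends it (7.6). Only section 7.6 says that specimens are still collected after the stop, and it gives no time. Section 9.2 specifies an intention-to-treat primary comparison.

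**The concern.** An intention-to-treat comparison of a marker at one time point needs a sample from every randomised patient at a comparable time. Here the one operational window moves with the end of infusion. For most reasons for stopping, the plan does not say whether a second sample is taken at all. Section 7.4 is headed as discontinuation of the study rather than of the infusion, so staff could reasonably take it to end sampling as well.

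Two kinds of harm are possible:

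- **Early samples.** If dextrose changes the course of IL-6, as the trial hypothesises, samples taken early can dilute the difference even when both arms stop equally often. If one arm stops more often or sooner, early samples can also bias it.
- **Missing samples.** These can bias the comparison when their frequency differs by arm. They can also do so at equal frequency if the reasons differ by arm.

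**Working it through.** The plan gives no derived figure for the draw time, so the check is interval arithmetic on its stated times, followed by a comparison of the stop provisions.

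**Inputs.** Planned infusion: 24 h (5.3.3). Draw window: 2 h before to 0.5 h after the end of infusion (5.4.6). Delay *d* from randomisation to infusion start: 0 to 4 h, because randomisation follows baseline testing (5.2.3) and the baseline draw is at most 4 h before the start (5.4.3).

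**1. Uninterrupted infusion.** The window after randomisation is *d* + 24 − 2 to *d* + 24 + 0.5.

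- *d* = 0: 22 to 24.5 h
- *d* = 2: 24 to 26.5 h
- *d* = 4: 26 to 28.5 h

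Against the synopsis time of 24 h, that is from 2 h early to 4.5 h late.

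**2. Section 5.4.6 against 6.3.2.** The window is 2 + 0.5 = 2.5 h long. Only the last 0.5 h (0.5/2.5 = 20%) falls after completion, as 6.3.2 requires.

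**3. Paused infusion.** Section 7.1.1 allows pause and restart but does not say whether lost time is made up. If a pause of *p* hours is made up, the window becomes *d* + *p* + 22 to *d* + *p* + 24.5. The 28.5 h in step 1 is therefore not an upper limit.

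**4. Early stop at *s* hours, with 5.4.6 read literally.** The window is *s* − 2 to *s* + 0.5 h after the start. A draw at the stop is 24 − *s* h before the 24-hour point, counted from infusion start. The values of *s* are chosen for illustration.

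| Stop (h) | Literal window (h after start) | Draw at the stop is early by (h) |
|---|---|---|
| 4 | 2 to 4.5 | 20 |
| 8 | 6 to 8.5 | 16 |
| 12 | 10 to 12.5 | 12 |
| 18 | 16 to 18.5 | 6 |

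An unplanned stop is not known in advance, so in practice only the part of the window from the stop onward can be used.

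**5. What is stated about the second draw, by reason for stopping.**

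| Event | Sampling continues? | Time given? |
|---|---|---|
| Tube feeds started (7.6) | Yes | No |
| Treating physician stops the infusion (5.3.2) | Not stated | No |
| Ketoacidosis or hyperosmolar syndrome (7.1.2) | Not stated | No |
| Section 7.4 criteria | Not stated; heading ambiguous | No |
| Pause for emesis (7.1.1) | Not stated | No; effect on end of infusion not stated |

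**6. Clocks used elsewhere.** The mid-intervention assessment counts from infusion start (5.4.5), while glucose monitoring starts at randomisation (6.3.1). The missing time zero in Table 5-1 therefore cannot be settled by analogy.

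**The case against.** The best defence is that a fixed 24-hour clock is largely in the text already. Table 5-1 places the draw at 24 hours. Section 6.3.2 ties it to the intervention period, not to the infusion, and section 7.5 separates the two by recording the "total amount of time that enteral study infusion was successfully administered during the 24 hour intervention period". On that reading, a patient stopped at 6 hours still has a period ending at 24. The companion sample follows the same clock: "At 24 hr, we will obtain a gastric aspirate" (6.3.3). Section 7.6 shows that stopping the infusion does not by itself end sampling, and intention-to-treat implies that everyone's sample is wanted.

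As evidence of intent, this stands. It does not close the gap. The only window staff can apply is anchored to the end of infusion. The authors also thought continued collection worth stating for one reason for stopping and left it out for the rest.

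A reader might infer more than the documents support:

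- *That the sections define rival primary endpoints.* They do not. Sections 5.0 and 6.3.2 fit a nominal 24-hour draw, and for uninterrupted infusions the spread is a few hours.
- *That early stoppers will be sampled early and the result is biased in a known direction.* The documents do not show that stopping will differ by arm. Blinding (5.2.4) and exclusion of ketoacidosis and hyperosmolar syndrome at entry (5.1.2) limit such a difference. They do not rule it out, since glucose above 500 mg/dL and emesis are among the section 7.4 triggers. The direction would also depend on whether IL-6 is rising or falling, which is not stated.
- *That there is no harm unless stopping rates differ by arm.* This is too lenient, because dilution and missingness for different reasons can occur at equal rates.

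**Conclusion.** The point holds as a minor to moderate fault. The timing statements conflict and must be reconciled, but for an uninterrupted infusion the mismatch is about 2 h early to 4.5 h late against 24 h from randomisation. That range assumes a delay of 0 to 4 h before the infusion starts. It is not a firm bound, because the handling of pauses is unstated.

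The substantive part is early stopping. For every reason except tube feeding the plan does not say whether the primary sample is taken, and for every reason it does not say when. A literal reading of sections 5.4.6 and 7.4 could have these patients sampled many hours early or not at all, which can dilute or bias the primary comparison. The size cannot be estimated: the plan gives no early-stop rate, no IL-6 time course in these patients and no IL-6 standard deviation. A nominal 24-hour draw was probably intended, and this keeps the severity down.

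**What to change.** Reconcile the synopsis, sections 5.0, 5.4.6 and 6.3.2, and Table 5-1 to one time zero and one window. Two choices would work:

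- 24 h from randomisation, which exists for every randomised patient; or
- 24 h from infusion start, with the synopsis changed to match.

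Then make these changes:

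- State that the draw is taken at that time whether or not the infusion was interrupted or stopped early.
- Extend the section 7.6 sentence on continued specimen collection to every early stop except withdrawal of consent.
- Say in section 7.4 that stopping the infusion does not end research sampling.
- Record the actual time of each draw.

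The clinical stopping criteria stay as they are. The cost is mainly in wording. Some draws will be taken after the infusion has already stopped, and a few patients who might otherwise have been missed will be sampled, at about 10 mL of blood each (6.3.2).

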## 2.0 GLOSSARY

**Cytokine:** a cell-signaling protein released by immune cells in response to infection or injury

**Enteral Nutrition:** feeding or nutrients that are provided directly into the stomach or intestines

**Glucagon-like peptide 1 (GLP-1):** an incretin hormone released in the distal intestines and colon

**Glucose-dependent insulintropic peptide (GIP):** an incretin hormone released in the proximal small intestine

**Interleukin-1 beta (IL-1 $\beta$ ):** a pro-inflammatory cytokine involved in the pathogenesis of sepsis

**Interleukin-6 (IL-6):** a pro-inflammatory cytokine involved in the pathogenesis of sepsis

**Incretin:** an intestine-derived hormone released in response to enteral nutrients with a primary function of potentiating insulin release from the pancreas

**Microbiome:** the community of micro-organisms including all bacteria, viruses, and fungi that reside within animals and humans

**Parenteral Nutrition:** feeding or nutrients that is provided intravenously

**Sepsis:** a syndrome characterized by a pro-inflammatory response to infection

**Tumor Necrosis Factor alpha (TNF- $\alpha$ ):** a pro-inflammatory cytokine involved in the pathogenesis of sepsis

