Our data suggest that activation of incretin hormone pathways plays a vital role in mediating the beneficial effects of enteral dextrose in endotoxemic mice. Infusion of low-level continuous enteral dextrose in our model increases circulating levels of the incretin hormone GIP. When incretin signaling is blocked with pharmacologic agents, the beneficial effects of enteral dextrose on glucose tolerance, insulin secretion, and inflammation are lost. Blocking GIP, which is released more proximally in the intestine, appears to be more detrimental than blocking GLP-1 in our model. Further supporting the therapeutic potential of incretin hormones, exogenous infusions of GLP-1 and GIP were able to rescue glucose tolerance, improve insulin release, and decrease inflammation in endotoxemic mice receiving intravenous dextrose, the group of mice that had previously demonstrated the worst glucose tolerance. Thus, targeting the endogenous incretin hormone pathway in septic patients with the use of enteral dextrose infusion may provide a novel means of maintaining euglycemia and modulating the systemic inflammatory response while preventing the hypoglycemia that is often associated with exogenous insulin administration.

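### Sections 5.4.6 and 6.3.2 disagree on when the second research blood draw is taken, and a draw after the infusion stops may understate the hormone response in the dextrose arm

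*Combined protocol and SAP*

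**What the plan says.** Section 5.4.6 gives the window for the end-of-infusion sample: "Second research blood draw (up to 2 hours prior to the end of infusion or ½ hour after". That is 2.5 hours wide, with 2 hours before the stop and half an hour after it. Section 6.3.2 describes the same draw differently. It states that "Blood will be drawn for plasma and serum at two time points", the second being "after the completion of the intervention period", with no option before the stop and no upper limit.

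Table 5-1 also shows only two research blood draws, at baseline and 24 hours. The secondary outcomes in section 5.0 that need research blood include "measures of insulin, C-peptide, and the incretin hormones glucose-dependent insulinotropic peptide (GIP) and glucagon-like peptide-1 (GLP-1", so each has exactly one post-baseline value.

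The glossary defines an incretin as "an intestine-derived hormone released in response to enteral nutrients". The supporting mouse evidence in section 4.1.5 concerns levels under a running infusion: "Infusion of low-level continuous enteral dextrose in our model increases circulating levels of the incretin hormone GIP". Under section 5.3.1 the dextrose arm receives 10 mL per hour for 24 hours, and the placebo arm receives free water with no enteral calories.

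Section 9.2 plans a t-test or non-parametric test for secondary continuous outcomes, with no account taken of draw time. No section requires the infusion to be running at the draw. Section 7.6 keeps collecting specimens when the infusion is stopped early for tube feeds, without saying when.

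**The concern.** There are two problems. The first is textual: a draw one hour before the pump stops complies with 5.4.6 and not with 6.3.2, so staff cannot tell which rule governs.

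The second concerns what the sample measures. If the hormones respond to nutrients reaching the gut, a sample taken after delivery ends may catch a response that is already falling. Only the dextrose arm has a study-induced nutrient response to lose, so such samples pull the between-arm difference toward zero.

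Increasing incretin hormones is one of the four effects in the trial hypothesis (section 3.1), and section 4.1.5 treats the incretin pathway as the likely mediator. A null hormone comparison could be read as evidence against the mechanism when part of the explanation was draw time. Because the protocol does not ask for the interval between stop and draw, this could not be examined afterwards.

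**Working it through.** The documents state no hormone effect size, SD, decay rate or power, so there is no figure of the plan's own to reproduce. The passages can be compared directly, and the possible loss can be shown as a range.

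**1. The passages side by side**

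| Source | Second draw | Before the stop? | After the stop? |
|---|---|---|---|
| 5.4.6 | 2 h before to ½ h after end of infusion | allowed | allowed, to 30 min |
| 6.3.2 | after the intervention period | not provided for | required if read literally, no limit |
| Table 5-1 | 24 hrs | not specified | not specified |

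Share of the 5.4.6 window after the stop: 0.5 / 2.5 = 20%.

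**2. Inputs for the illustration**

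- From the documents: 36 per arm (section 1.0) and alpha 0.05 (section 9.1, stated for IL-6).
- Assumed: a two-sided test; exponential decay of the dextrose-induced increment starting when the pump stops; half-lives of 5, 10, 20 and 60 min; SD unchanged; post-stop draws uniform over 0–30 min.
- Reference effect: d = 0.775, the standardized difference that a two-sample t-test detects with 90% power at 36 per arm.

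**3. Formulas**

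- Fraction of the increment left at 30 min = 0.5^(30/h), where h is the half-life.
- Mean fraction m over 0–30 min = (1 − 0.5^(30/h)) / (30 × ln 2 / h).
- With a share p of draws after the stop, the retained difference is (1 − p) + p × m, and power is that of the t-test at 0.775 times this factor.

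Example, h = 5 and p = 0.2: 0.5^6 = 0.016; m = 0.984 / 4.159 = 0.237; retained = 0.8 + 0.2 × 0.237 = 0.847; d = 0.775 × 0.847 = 0.656; power 78%.

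**4. Results with draws spread evenly over the 5.4.6 window (p = 0.2)**

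| Half-life (min) | Left at 30 min | m | Retained difference | Power (from 90%) |
|---|---|---|---|---|
| 5 | 2% | 0.237 | 0.847 | 78% |
| 10 | 13% | 0.421 | 0.884 | 82% |
| 20 | 35% | 0.622 | 0.924 | 85% |
| 60 | 71% | 0.845 | 0.969 | 88% |

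**5. Sensitivity**

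- If the response holds for 15 min after the stop before decaying, the same p = 0.2 case gives 86% to 89% power. If it holds for 30 min, nothing is lost within the 5.4.6 window.
- If every draw fell after the stop, within 30 min, power would be 12%, 28%, 52% and 78% for the four half-lives. This takes the placement from 6.3.2 and the 30-minute cap from 5.4.6; neither section states both.

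Only the shrinking mean difference is modelled. Any extra variance from mixing on- and off-infusion samples is not included.

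**The case against.** A reader might infer from 6.3.2 that every hormone sample will be taken off-infusion, and that the 12% to 78% figures are what the trial should expect. The documents do not support that. Section 5.4.6 is the specific timing rule, and the amendment log records that time frames were added to section 5.4 in Version 3.0. Section 6.3.2 is looser throughout: it puts the first draw at randomization, where 5.4.3 allows up to 4 hours before the infusion. Under 5.4.6, 80% of the window precedes the stop, and nothing says draws will cluster late. This objection stands, and it limits the expected loss to the smaller range.

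A reader might also infer that the stimulus ends when the pump does. That is not established either. The solution is given by gastric tube, section 4.1.6 expects absorption in the jejunum, and the same section mentions dysmotility from sedatives. Dextrose left in the stomach could sustain the response for some time. This also stands, and since every half-life is an assumption, material harm is not demonstrated from the documents.

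Further, the outcomes are secondary, no power is claimed for them, and the expected bias is toward no difference. Tube feeds started during the period can raise the hormones in either arm, so draw timing is not the only disturbance. A draw before the stop also cannot be guaranteed when the infusion ends unexpectedly (sections 7.1, 7.4 and 7.6).

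None of this resolves the conflict between the two sections or gives a scientific reason for the post-stop half hour.

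**Conclusion.** The conflict between 5.4.6 and 6.3.2 is plain on the text. The consequence is a possible, not a demonstrated, understatement of the GIP, GLP-1, insulin and C-peptide response in the dextrose arm.

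With draws spread evenly over the 5.4.6 window, an effect with 90% power on-infusion would keep about 78% to 88%. That rests on assumed half-lives of 5 to 60 min, decay from the moment of the stop, an unchanged SD and a two-sided test at 0.05. Continued gastric delivery would make the loss smaller. Clustering of draws after the stop would make it larger.

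It would go too far to say that a null incretin result would be uninformative. Severity: COULD. It is worth correcting because the correction is nearly free.

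**What to change.** - In 5.4.6, place the planned second draw within the existing 2 hours before the scheduled end of infusion, with the infusion running, and delete the half-hour allowance after the stop. Reword 6.3.2 to match.
- Record the draw time and the time the infusion stopped, so that the interval is known for every participant.
- Keep all samples in the intention-to-treat comparison, including those taken after unplanned early stops.
- An analysis without off-infusion samples may be added as supportive only. It excludes patients on an event after randomization, such as intolerance or early feeding, and so is not a clean randomized comparison.

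Cost: wording changes in two sections and two recorded times. The draw window narrows from 2.5 hours to 2 hours, so some late draws will fall outside it. No extra blood or visits are needed.
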